6.5.4. Death Date

Missing or partial death dates will not be imputed.

6.5.5. Pharmacokinetic Data

6.5.5.1. Handling of Missing Concentrations

Missing concentrations before the first dose of study treatment will be set to 0 in the analysis. A concentration is deemed missing if the PK sample is not collected, or the PK sample is collected but the concentration is not reportable.

In addition:

- If ≤2 samples have concentrations ≥LLQ, none of the PK parameters will be derived.
- If pre-dose concentrations are missing at a steady-state visit, PK parameters associated with that visit will not be derived with the exception of C_{max} and T_{max} .

Since the protocol allows a ± 30 minutes window for the 7-hour PK sample collection, if the end time of the predefined area under the concentration-time curve falls outside the range of the available data then:

- the AUC_{0-last} will be used to represent AUC₀₋₇, if $T_{last} \ge 6.5$ h.
- AUC₀₋₇ will not be reported, if $T_{last} < 6.5$ h.

6.5.5.2. Incomplete Dosing Information

Samples associated with incomplete dosing information (ie, missing dosing date, dosing time, actual dose received, and/or dosing schedule) will be excluded from the analysis. The missing dosing information will not be imputed.

6.5.5.3. Missing Sampling Dates or Times

Samples associated with missing sample dates and/or times will be excluded from the analysis. The missing sampling dates and/or times will not be imputed.

6.5.5.4. Incomplete Concentration-time Data

Subjects who have incomplete concentration-time profiles (ie, missing concentrations at more than one scheduled time point) may be excluded from the PK analysis set. The decision will be made by the unblinded clinical pharmacologist before the study is unblinded for the analysis of the primary endpoint.

7. STATISTICAL ANALYSES

7.1. Subject Disposition

For all subjects screened in the study, the following will be summarized:

- Number of subjects screened in the study
- Frequency (number and percentage) of subjects who discontinued the study before randomization, overall and by reason for discontinuation. Percentages will be calculated based on the number of subjects screened in the study.

In addition, the frequency of subjects in each of the analysis sets described in Section 5 will be summarized by treatment arm. Percentages will be calculated only for analysis sets that are a subset of the FAS or a subset of the safety analysis set.

The following summaries will be presented by treatment arm based on the FAS or (for the summaries associated with the OLE Period only) the OLE analysis set:

- Frequency of subjects in each randomization strata and combination of randomization strata (per IXRS)
- Frequency of subjects randomized in each geographic region, country, and site
- Frequency of subjects randomized and not treated, overall and by reason for discontinuation
- Frequency of subjects who completed the Double-blind Period
- Frequency of subjects with study drug ongoing in the Double-blind Period
- Frequency of subjects who discontinued study drug in the Double-blind Period, overall and by the reason for discontinuation of study drug
- Frequency of subjects who completed the OLE Period
- Frequency of subjects with study drug ongoing during the OLE Period
- Frequency of subjects who discontinued study drug in the OLE Period, overall and by the reason for discontinuation of study drug
- Frequency of subjects who completed the safety follow-up period
- Frequency of subjects ongoing in the safety follow-up period
- Frequency of subjects who discontinued the safety follow-up period, overall and by the reason for discontinuation

- Frequency of subjects who completed the study
- Frequency of subjects ongoing in the study
- Frequency of subjects who discontinued the study, overall and by reason for discontinuation; the reason for discontinuation will be derived as the reason associated with the earliest epoch that was discontinued.

The frequency of subjects with disposition reason, in each epoch, due to reasons associated with COVID-19 will further be summarized under the main reason for discontinuation.

In addition, cross-tabulation of subjects randomized (mitapivat, matched placebo) vs subjects who have received at least 1 dose of study drug (mitapivat, matched placebo) in the Double-blind Period will be performed.

Disposition for all screened subjects and randomization data will be provided in by-subject listings.

7.2. **Protocol Deviations**

All major protocol deviations that impact the safety of the subjects, the conduct of the study, or the evaluation of the study results will be reported by treatment arm based on the FAS or (for the summaries associated with the OLE Period only) the OLE analysis set. These will include:

- Subjects randomized despite not satisfying the eligibility criteria
- Subjects who develop withdrawal criteria while on the study but are not withdrawn
- Subjects who receive a study drug different from that assigned at randomization
- Subjects who are randomized under the wrong stratification factor(s)
- Subjects who receive an excluded concomitant medication

In addition, for each category of major protocol deviations, those related to COVID-19 will be summarized.

Major protocol deviations will be provided in a by-subject listing.

7.3. Demographic and Other Baseline Characteristics

The following summaries will be presented by treatment arm and overall based on the FAS or (for the summaries associated with the OLE Period only) the OLE analysis set, unless otherwise specified.

7.3.1. Demographics and Physical Measurements

Demographic characteristics and physical measurements at baseline will be summarized as follows:

• Demographic characteristics

- Sex: male, female (child-bearing potential status will be summarized for female subjects), unknown
- Race: American Indian or Alaska Native, Asian, Black or African American, Native Hawaiian or other Pacific Islander, White, multiracial, unknown, not reported
- Ethnic origin: Hispanic or Latino, not Hispanic or Latino, not reported
- Age (years): summary statistics
- Age categories:
 - <65 years, ≥ 65 years
 - <35 years, ≥ 35 years
- Physical measurements
 - Height (cm)
 - Weight (kg)
 - BMI (kg/m^2)

Demographic data for all screened subjects will be provided in a by-subject listing.

7.3.2. Disease Characteristics

In addition to randomization stratification factors (Section 7.1) and baseline for diseaserelated clinical laboratory assessments (Section 7.6.3.2,

, the following baseline characteristics of the underlying disease will be summarized based on the data entered in the eCRF:

- Pretransfusion Hb threshold. A pretransfusion Hb threshold will be determined for each subject based on transfusion history. The pretransfusion Hb threshold is defined as the mean of all documented pretransfusion Hb concentration values recorded for the RBC transfusions administered during the 24-week period before randomization
- 24-week baseline transfusion burden as defined in Section 6.3.4.1 (≤12 RBC units, >12 RBC units)
- Splenectomy status (Yes, No; if Yes, age of splenectomy)
- Prior cholecystectomy status (Yes, No; if Yes, age of cholecystectomy)
- Prior Iron chelation status (Yes, No); the status is "Yes" if a subject has received chelation therapy within 1 year (365 days) before randomization
- Prior hydroxyurea status (Yes, No)
- DXA scan results by location (hip and spine): BMD and their corresponding Tscores and Z-scores. Frequency of subjects with worst T-score in 3 categories (≤-2.5, >-2.5-<-1, ≥-1.0) by location and across the two locations.

Data on disease characteristics will be provided in by-subject listings.

7.3.3. Medical and Surgical History

Medical and surgical history will be summarized in frequency tabulations according to the latest version of the Medical Dictionary for Regulatory Activities (MedDRA) by System Organ Class (SOC) and Preferred Term (PT).

Medical and surgical history will be provided in by-subject listings.

7.3.4. **Prior Therapies**

The following summaries will be presented by treatment arm and overall based on the safety analysis set.

Prior medications are defined as medications (from the "Prior and Concomitant Medications" eCRF) that are started before the start of study treatment.

All non-study medications will be coded according to the Anatomical Therapeutic Chemical (ATC) code and PT using the latest version of the World Health Organization (WHO) Drug Dictionary. All prior medications will be summarized in frequency tabulations according to the WHO ATC third level and PT.

Prior procedures are defined as procedures (from the "Prior and Concomitant Procedures" eCRF) that are started before the start of study treatment.

The prior procedures will be coded according to the latest version of the MedDRA by SOC and PT and will be summarized in frequency tabulations by SOC and PT.

Prior medications and prior procedures will be provided in by-subject listings.

7.4. Exposure to Study Drug and Compliance

The following summaries will be presented by treatment arm based on the safety analysis set for the Double-blind Period using "Prescribed Dose", "First Dose of Study Medication (Double-blind Period)", and "Study Drug Dispensation and Return" eCRFs; and the OLE analysis set for the OLE Period using the "Prescribed Dose", "First Dose of Study Medication (Open-label Extension Period)", and "Study Drug Dispensation and Return" eCRFs.

Subjects will receive 100 mg BID mitapivat or matched placebo for oral administration. Subjects who discontinue study drug should undergo the recommended dose taper. Study drug dose and recommended dose taper are provided in Table 4.

Table 4:	Study Drug Dose and Recommended Dose Taper Regimen
----------	--

Level	Dose	Schedule
Full dose	100 mg	BID
Taper dose	100 mg	QD for 7 days, then discontinue study drug

Abbreviations: BID = twice daily; QD = once daily

7.4.1. Treatment Duration and Exposure

Duration of exposure to study drug will be summarized as a continuous variable as well as in categories.

• Duration of exposure (days)=(last dose date-first dose date+1)

Duration of exposure (weeks)=(last dose date-first dose date+1)/7

- Duration of exposure (years)=(last dose date-first dose date+1)/365.25
- Double-blind Period: the categories will be >0-6, >6-12, >12-24, >24-36, >36-48, and >48 weeks
- OLE Period: the categories will be >0-0.5, >0.5-1, >1-2, >2-3, >3-4, >4-≤5, and >5 years.

Compliance will be summarized based on percentage of tablets taken, where

• Percentage of tablets taken =100×(total number of tablets administered)/(total number of tablets intended)

Total number of tablets administered = total number of tablets dispensed – tablets returned

Duration of prescription = end date of prescription-start date of prescription +1

Total number of tablets intended = sum of number of tablets intended over all prescription periods.

Number of tablets intended during each prescription period = prescribed dosing frequency \times number of tablets intended for each administration \times duration of the prescription. Prescribed dosing frequency takes value of 1 and 2 for QD and BID, respectively

Percentage of tablets taken will be summarized by treatment arm. The frequency of subjects whose compliance is <80%, 80-100%, >100-120%, and >120% will be summarized.

7.4.2. Dose Modifications

The summary of dose modifications will include:

- The frequency of subjects with at least 1 dose reduction
- The reason for dose reduction
- The frequency of subjects with at least 1 interruption of study drug
- The reason for interruption of study drug

Dose reduction is defined as a prescribed non-zero daily dose that is lower than the planned dose (200 mg daily). An interruption of study drug is defined as a prescribed daily dose of 0 mg.

The reason for an interruption of study drug or dose reduction will be derived based on the "Reason for prescribed dose change" in the "Prescribed Dose" eCRF.

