³ If allowed by local institutional guidelines, and at the discretion of the Investigator and the subject, the subject can complete some visits and study-related assessments at home. These visits (Investigator Assessment only) will be conducted by the Investigator (or designee) (see Section 8).

⁴ After completing the study visit at Week 312, subjects should begin the dose taper.

⁵ Pregnancy testing should occur more frequently as clinically indicated (ie, if there is suspicion of pregnancy) or if required by local regulations. A serum or urine pregnancy test will be performed locally for WOCBP at the Safety Follow-up visit.

⁶ DXA scan of the hip and spine.

- ⁸ Vital signs include systolic and diastolic blood pressure, pulse rate, and body temperature. Weight will also be recorded. Vital signs should be measured after 5 minutes of recumbency, and before blood sample collection.
- ⁹ Hematology includes a complete blood count (Hb, HCT, MCHC, MCH, MCV, RBC count, nucleated RBCs, RDW-CV, % reticulocyte count, absolute reticulocyte count, and platelet count) with WBC count and differential (neutrophils, basophils, lymphocytes, and monocytes).
- ¹⁰Clinical chemistry includes albumin, BUN or urea, total calcium, CO₂ or bicarbonate, chloride, creatinine, magnesium, magnesium, phosphorus, potassium, sodium, total protein, and uric acid.
- ¹¹Liver tests include ALP, ALT/SGPT, AST/SGOT, and bilirubin (direct/conjugated, indirect/unconjugated, and total).
- ¹²Lipid panel includes nonfasting HDL-C, LDL-C, total cholesterol, and triglycerides.
- ¹³ Sex hormones include nonfasting estradiol, estrone, and testosterone (free and total). If possible, blood samples should be collected in the morning. A highly sensitive LCMS assay should be used to analyze samples.
- ¹⁴Iron panel includes iron, serum ferritin, transferrin, transferrin saturation, and total iron binding capacity.

¹⁷Study drug will be dispensed at every visit. Subjects must return study drug bottles (including empty bottles) and unused tablets at each visit to the clinical study center. The morning dose of study drug will be administered at the clinical study center during in-person visits to the clinical study center.

¹⁸ Adverse events and SAEs will be collected throughout the study.

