6.3.5. On-Treatment Period

The on-treatment period starts on the date of the start of study treatment and ends 28 days after the end of study treatment (including dose taper period).

Within the on-treatment period, there are two distinct treatment periods:

- Double-blind on-treatment period starts on the date of the start of study treatment and ends
 - 28 days after the end of study treatment, for subjects who discontinue study treatment during the Double-blind Period of the study
 - Before the start of the OLE treatment period, for subjects who continue onto the OLE Period of the study

• OLE on-treatment period applies only to subjects who complete the Doubleblind Period of the study, and starts with the first dose of open-label mitapivat in the OLE Period and ends 28 days after the end of study treatment.

For subjects who receive mitapivat in the OLE Period, assessments or events occurring on the date of first dose of mitapivat in the OLE Period will be included in the analysis of the data from the double-blind on-treatment period, except for AEs and concomitant medications reported for subjects in the placebo arm which will be included only in the analysis of the data from the OLE on-treatment period.

Data listings will include all assessments and events, with those that occur outside of the on-treatment period flagged.

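### The SAP's dose-reduction rule takes in the once-daily discontinuation taper, so recorded tapers would be tabulated as dose reductions

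*SAP*

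**What the plan says.** SAP 7.4.2 defines the category purely by amount: "Dose reduction is defined as a prescribed non-zero daily dose that is lower than the planned dose (200 mg daily"). An interruption is a prescribed daily dose of zero. The first output listed is "The frequency of subjects with at least 1 dose reduction". The reason is a separate item, taken from a field on the Prescribed Dose eCRF; the count is not restricted by reason.

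SAP 7.4 gives the regimen: "Subjects will receive 100 mg BID mitapivat or matched placebo for oral administration". It adds: "Subjects who discontinue study drug should undergo the recommended dose taper". SAP Table 4 lists the taper dose as 100 mg, "QD for 7 days, then discontinue study drug". The on-treatment period in SAP 6.3.5 "ends 28 days after the end of study treatment (including dose taper period"), so taper days lie inside it.

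The protocol also sends OLE completers to the taper. Table 2, footnote 4, says: "After completing the study visit at Week 312, subjects should begin the dose taper".

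Protocol 6.7 allows dose modifications for two causes, excessive Hb response and drug-related adverse events (AEs). It describes the taper separately, as part of stopping drug.

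**The concern.** A dose-reduction row is normally read as a tolerability signal: how many subjects could not stay on the planned dose. A taper on the way off drug is a different event, and the protocol treats it as one. The SAP rule has no term that separates the two.

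In the Double-blind Period, tapers would be added to true reductions. If tapering were more common in one arm, that arm would show more dose reductions even if true reductions were equal. In the OLE, where completers taper by design, the row would mostly reflect who reached the end of the study and would say little about real modifications.

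**Working it through.** **1. The plan's own threshold.** The full dose in SAP Table 4 is 100 mg twice daily: 100 × 2 = 200 mg a day. This matches the planned dose in SAP 7.4.2.

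**2. The taper under the rule.** The taper is 100 mg once daily: 100 × 1 = 100 mg a day. The rule is 0 < prescribed daily dose < 200 mg. Since 0 < 100 < 200, the taper qualifies, at 100/200 = 50% of the planned dose.

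**3. Whether another provision removes it.** None does.
- SAP 6.3.2 ends treatment at the latest non-zero dose, and SAP 6.3.5 keeps the taper inside the on-treatment period.
- SAP 7.4.1 handles prescriptions by period, with frequency 1 for once daily and 2 for twice daily. Once-daily prescriptions are thus an expected kind of record.
- The reason is tabulated next to the count and does not filter it.

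**4. Who is reached.**
- Double-blind: subjects who stop with a taper. Those who continue take open-label drug on the evening of the Week 48 visit (protocol Table 1, footnote 28), with no taper between. Abrupt stopping without a taper is foreseen in protocol 6.1; those subjects are not reached.
- OLE: those who discontinue with a taper, and completers who taper after Week 312.

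**5. Size.** The documents give neither the true reduction rate *m* nor the share who taper *t*, so both are assumptions here. If the two are independent, the tabulated share is *m* + *t* − *mt*.

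| Period | *m* | *t* | Tabulated |
|---|---|---|---|
| Double-blind, low | 3% | 5% | 0.03 + 0.05 − 0.0015 = 7.85% |
| Double-blind, middle | 5% | 10% | 0.05 + 0.10 − 0.005 = 14.5% |
| Double-blind, high | 10% | 15% | 0.10 + 0.15 − 0.015 = 23.5% |
| OLE, low | 5% | 70% | 0.05 + 0.70 − 0.035 = 71.5% |
| OLE, high | 10% | 100% | 100% |

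In the middle case, with the 160 subjects planned for mitapivat, the table shows 0.145 × 160 = 23.2, about 23 subjects, instead of 0.05 × 160 = 8. Independence is not essential. With complete overlap the figure is max(*m*, *t*) = 10% (16 subjects). With no overlap it is *m* + *t* = 15% (24 subjects).

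**6. Between arms.** Suppose *m* = 5% in both arms, with *t* = 15% in one and 5% in the other. The table shows 19.25% against 9.75%. The gap of 9.5 points arises from tapering alone: (0.15 − 0.05) × (1 − 0.05) = 0.095. These rates are also assumed, and the documents give no reason to expect either direction.

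**7. A record with the same dose but another meaning.** Protocol Table 7 prescribes 100 mg once daily for 7 days and then discontinuation after a second Grade 3 or any Grade 4 drug-related event. In dose and length this matches the Table 4 taper, but the protocol lists it as a dose modification for drug-related AEs. A correction based on dose and duration alone would remove both.

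**The case against.** The strongest objection is that the rule acts on prescriptions recorded on an eCRF that is not in the documents. If the taper is not entered there as a new prescription, the effect disappears. If the reason field has a taper or discontinuation option, a reader could see the inflation in the same summary. The condition stands and limits the claim. It does not repair the rule, because the SAP neither says that tapers are left off the form nor tells the programmer to drop them. A reason row would explain the count without correcting it.

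It can also be said that SAP Table 4 names full dose and taper dose as distinct levels, and that protocol 6.7 keeps modifications and tapers apart. That shows the likely intent, but SAP 7.4.2 does not carry it over.

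Three stronger readings are tempting.
- *Every subject who leaves drug is certain to be counted.* This depends on the unseen form. The taper is also only recommended, and abrupt stoppers and double-blind subjects who continue into the OLE do not have it.
- *Discontinuations are double-counted.* No summary adds reductions to discontinuations. SAP 7.1 reports discontinuation by reason, and one subject may properly appear in both tables.
- *The safety conclusions are distorted.* SAP 7.7.1 summarises treatment-emergent AEs leading to dose reduction and those leading to discontinuation separately, and protocol 9.2.1 has the action taken with study drug recorded for each event. A taper after stopping for a non-AE reason has no evident route into those tables.

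**Conclusion.** The point holds as a defect in a descriptive definition. As written, SAP 7.4.2 counts a recorded Table 4 taper as a dose reduction and so mixes discontinuation tapers with the modifications described in protocol 6.7. It rests on one assumption, that tapers are recorded on the Prescribed Dose eCRF.

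The numerical size cannot be taken from the documents; the ranges above show only what plausible inputs would do. The double-blind effect is confined to subjects who stop with a taper. The OLE effect could swamp the row, but that summary has no concurrent placebo group and belongs to the addendum report (SAP 2).

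The primary and key secondary analyses are untouched, as are the AE tables.

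**What to change.** Add to SAP 7.4.2:
- Prescriptions that form only the Table 4 discontinuation taper are not counted as dose reductions. The number of subjects with such a taper is shown on a separate row.
- Reductions made for excessive Hb response or drug-related AEs remain in the count, including those later followed by discontinuation.
- The protocol Table 7 seven-day once-daily step before discontinuation is shown on its own identified row and is not excluded, so that AE-driven modifications stay visible.

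Because the last of these cannot be told from a Table 4 taper by dose and length, the SAP should name the eCRF field that separates them, for example the reason for the prescribed dose change or the action taken for the AE. Confirm that this field exists before unblinding, so that the classification is not chosen after the arms are known.

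The cost is a few sentences in the SAP, two rows in a table shell and one check of the eCRF. This is an analysis classification only and changes no dose or clinical rule.

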7.5. Concomitant Therapies

The following summaries will be presented by treatment arm based on the safety analysis set for the Double-blind Period and the OLE analysis set for the OLE Period.

Concomitant medications are defined as non-study medications (from the "Prior and Concomitant Medications" eCRF) that are started during the on-treatment period or are started before the start of the study treatment and end or remain ongoing during the on-treatment period.

All non-study medications will be coded according to ATC code and PT using the latest version of the WHO Drug Dictionary. All concomitant medications will be summarized in frequency tabulations according to WHO ATC third level and PT.

Concomitant procedures are defined as procedures (from the "Prior and Concomitant Procedures" eCRF) that are started during the on-treatment period or are started before the start of the study treatment and end or remain ongoing during the on-treatment period.

The concomitant procedures will be coded by the latest version of MedDRA by SOC and PT and will be summarized in frequency tabulations by SOC and PT.

Concomitant medications and concomitant procedures will be provided in by-subject listings.

